Subjects who meet inclusion and exclusion criteria for eligibility will undergo Baseline assessments at Week 0, including hair examination, clinical assessments (SALT and eyebrow/eyelash scores), additional skin assessments if he/she concurrently has atopic dermatitis (EASI, IGA, SCORAD), review of medications, standardized clinical photography (optional), questionnaires (AASIS and AA-QLI), and urine pregnancy testing (where applicable). Blood samples and skin biopsies will be collected for mechanistic studies (described below), as well as DNA, RNA, and protein analyses. Two 4.5 mm scalp biopsies will be performed at Baseline: one from an area with active AA (i.e. the peripheral edge of a scalp lesion with active hair loss) and one from an adjacent uninvolved area of the scalp. If the subject has 100% hair loss at Baseline exam, a single biopsy of the posterior scalp will be collected. For subjects with concomitant AD, an additional lesional skin biopsy will be collected from an active AD lesion as outlined in the schedule of events. At this Baseline visit, subjects will undergo randomization and be given their first injection of the study drug (dupilumab or placebo).

The first dose will be a loading dose of 600mg (given as two injections of dupilumab or placebo), provided in the clinic (including a 30-minute post-injection follow-up), followed by the patient's weekly self-administration of 300 mg (one injection of dupilumab or placebo) at home (assuming the patient and the care team feel that the patients is ready to self-inject at home).

After sufficient training and when the subject feels comfortable to self-inject, the subject will be provided with the study drug (dupilumab or placebo), and will receive weekly dosing through Week 24.

During Phase I and II of the study, subjects will return for visits every four weeks for repeat clinical assessments, medication reviews, and monitoring for adverse events. Female subjects will undergo a urine pregnancy test (where applicable) at each of these visits.

At Week 48, if subjects want to seek other treatment options (including commercially available dupilumab) for AA, they may do so through their own dermatologist/physician. Any treatments will be documented as concomitant medications.

INDEPENDENT EXPERT ASSESSMENT:

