- Dispense/administer study drug (subjects previously on dupilumab will receive 1 injection of 300 mg dupilumab and 1 injection of placebo to maintain the blind of the study; subjects previously on placebo will receive 2 injections of 300 mg dupilumab). All subjects should be observed for 30 minutes following the injection to preserve the blind.
- Record concomitant medications and adverse events

Visit 9 – Week 28

- Urine pregnancy test for all female subjects of child-bearing potential to confirm subject is not pregnant
- Obtain vital signs
- AA Clinical assessments (SALT, aaPGA, and eyebrow/eyelash)
- AD Clinical assessments, if applicable (EASI, IGA, SCORAD)
- Dispense/administer study drug
- Record concomitant medications and adverse events

Visit 10 – Week 32

- Urine pregnancy test for all female subjects of child-bearing potential to confirm subject is not pregnant
- Obtain vital signs
- AA Clinical assessments (SALT, aaPGA, and eyebrow/eyelash)
- AD Clinical assessments, if applicable (EASI, IGA, SCORAD)
- Dispense/administer study drug
- Record concomitant medications and adverse events

Visit 11 – Week 36

- Urine pregnancy test for all female subjects of child-bearing potential to confirm subject is not pregnant
- Obtain vital signs
- AA Clinical assessments (SALT, aaPGA, and eyebrow/eyelash)
- AD Clinical assessments, if applicable (EASI, IGA, SCORAD)
- Questionnaires (AASIS and AA-QLI)
- Standardized photographs
- Obtain CBC, CMP, LDH, CRP, and Total serum IgE
- Collect blood sample for mechanistic endpoints
- Dispense/administer study drug
- Record concomitant medications and adverse events

Visit 12 – Week 40

- Urine pregnancy test for all female subjects of child-bearing potential to confirm subject is not pregnant
- Obtain vital signs

- AA Clinical assessments (SALT, aaPGA, and eyebrow/eyelash)
- AD Clinical assessments, if applicable (EASI, IGA, SCORAD)
- Standardized photographs
- Dispense/administer study drug
- Record concomitant medications and adverse events

Visit 13 – Week 44

- Urine pregnancy test for all female subjects of child-bearing potential to confirm subject is not pregnant
- Obtain vital signs
- AA Clinical assessments (SALT, aaPGA, and eyebrow/eyelash)
- AD Clinical assessments, if applicable (EASI, IGA, SCORAD)
- Standardized photographs
- Dispense/administer study drug
- Record concomitant medications and adverse events

Visit 14 – Week 48

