Subjects are numbered sequentially. Each subject will be assigned a unique number and will keep this number for the duration of the study. Subject numbers will not be reassigned or reused for any reason. Subjects who discontinue or withdraw from the study before receiving a treatment assignment code, who re-enroll at a later time must be assigned a new subject number. Subjects should be identified only by their assigned identified code number. The investigator must maintain a subject master log linking the subject number to the subject's name. The investigator must follow all applicable privacy laws in order to protect a subject's privacy and confidentiality.

Randomization and Blinding

A subject who meets all of the inclusion and exclusion criteria will be assigned a randomization number pre-dose on day 0/baseline. The randomization number is distinct from the subject number.

After fulfilling the enrollment criteria, the subjects enrolled will be randomized in a 2:1 ratio of dupilumab to placebo.

The randomization for both sites will be performed by the designated Research Pharmacist/personnel at the Icahn School of Medicine utilizing the Web site <http://www.randomization.com> (or similar). The method uses random block sizes and randomly permuted blocks.

Approximately 60 subjects will be enrolled in the study in order to have at least 54 subjects complete (taking into account a 10% drop out rate). Subjects will be assigned a randomization number on day 0/Baseline. The randomization schema will be kept confidentially after generation.

INVESTIGATIONAL DRUG SUPPLY AND BLINDING:

Regeneron Pharmaceuticals will provide dupilumab 300 mg for 40 subjects in Phase I and for all 60 subjects during Phase II (a total of 25 doses in Phase I to those 40 subjects randomized to receive dupilumab, followed by another 24 doses in Phase II; a total of 24 doses in Phase II to the 20 subjects who received placebo in Phase I).

Eligible patients will receive a 600 mg SC dupilumab loading dose (300 mg initial dose, followed by a 300 mg loading dose) on day 0/Baseline, and then continue with 300 mg SC dupilumab once weekly starting on day 8. At Week 24, subjects previously on dupilumab will receive 1 injection of 300 mg dupilumab and 1 injection of placebo to maintain the blind of the study; subjects previously on placebo will receive 2 injections of 300 mg dupilumab. All subjects should be observed for 30 minutes following the injections at Baseline and at Week 24.

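### The Phase II dupilumab supply for former placebo subjects is stated as 24 doses each, but the Week 24 dosing text needs 25 syringes each

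*Combined protocol and SAP*

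**What the plan says.** The supply statement is in Investigational Drug Supply and Blinding. It covers 300 mg dupilumab for 40 subjects in Phase I and all 60 in Phase II, and gives three per-subject figures:

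- Dupilumab arm, Phase I: "a total of 25 doses in Phase I to those 40 subjects randomized to receive dupilumab".
- Dupilumab arm, Phase II: a further 24 for each of these subjects.
- Placebo arm, Phase II, where active drug starts only at the cross-over: "a total of 24 doses in Phase II to the 20 subjects who received placebo in Phase I".

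The dosing text on which these figures depend is as follows:

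- At baseline (Study Design Overview): "The first dose will be a loading dose of 600mg (given as two injections of dupilumab or placebo".
- After baseline (supply section, second paragraph), subjects "then continue with 300 mg SC dupilumab once weekly starting on day 8".
- At the Week 24 visit, the former dupilumab group gets one active and one placebo syringe, so that the blind is kept. For the other group the rule reads: "subjects previously on placebo will receive 2 injections of 300 mg dupilumab". Both halves of the rule appear in the supply section, in the Visit 8 list and in Table 1 footnote 12.

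Study Design Overview sets Phase II at 24 weeks, from Week 24 to Week 48. Neither the Visit 14 (Week 48) list nor the Week 48 column of Table 1 dispenses drug.

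**The concern.** The Phase I figure of 25 is one more than the 24 weekly dosing times in Weeks 0 to 23. The extra unit fits the second syringe of the baseline loading dose. Former placebo subjects also start active drug with two syringes, at Week 24, yet their Phase II figure is 24. That is the same as for subjects who receive only one active syringe at that visit. The two groups cannot both need 24 active syringes over the same weeks if one of them receives an extra active syringe at the start.

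The figure is operational: it sets how much active drug is to be provided. If it were applied as a fixed allotment per subject with no spare stock, each former placebo subject would have one 300 mg syringe fewer than the dosing passages call for before Week 48, which is a secondary time point. The sites must also account for all study drug, and would be reconciling against a number that the dosing text does not yield.

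**Working it through.** **Inputs.** The unit counted is one 300 mg injection. There are two injections at Week 0 and one a week after that. At Week 24 there is one active plus one placebo (former dupilumab) or two active (former placebo). The last dispensing visit is Week 44 and nothing is dispensed at Week 48, so the last weekly injection is read as Week 47. Nominal arm sizes are 40 and 20.

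**Step 1: reproduce the dupilumab-arm figures.**

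- Phase I: 2 (Week 0) + 23 (Weeks 1 to 23) = 25. Stated: 25. Starting the weekly doses on day 8 rather than day 7 also gives 25.
- Phase II: 1 active (Week 24) + 23 (Weeks 25 to 47) = 24. Stated: 24.

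**Step 2: apply the same count to former placebo subjects.**

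- Phase II: 2 active (Week 24) + 23 (Weeks 25 to 47) = 25. Stated: 24. The figure is not reproduced.

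**Step 3: totals.**

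- As stated: 40 × 25 + 40 × 24 + 20 × 24 = 1,000 + 960 + 480 = 2,440.
- By the dosing text: 40 × 25 + 40 × 24 + 20 × 25 = 1,000 + 960 + 500 = 2,460.
- Difference: 20 syringes, and 20 / 2,460 = 0.8%.

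**Step 4: does another unit rescue the 24?** Suppose a dose means a weekly dosing occasion, whatever the number of syringes.

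| Weeks assigned to each phase | Phase I | Phase II | Fits stated 25 and 24? |
|---|---|---|---|
| 0–23 and 24–47 | 24 | 24 | No: Phase I should be 25 |
| 0–24 and 25–47 | 25 | 23 | No: Phase II should be 24 |
| 0–24 and 24–47 | 25 | 24 | Only with Week 24 counted twice |
| 0–24 and 25–48 | 25 | 24 | Only with a Week 48 dose that Table 1 does not dispense |

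**Step 5: sensitivity.**

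- With 18 placebo subjects, the arm size in Sample Size Calculation, the gap is 18 × 1 = 18 syringes.
- If a Week 48 injection were given, the Phase II active counts would be 1 + 24 = 25 (former dupilumab) and 2 + 24 = 26 (former placebo). The groups would still differ by one, and neither figure of 24 would hold as a syringe count.

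**Step 6: all injections in Phase II, active and placebo.** Former dupilumab: 24 + 1 = 25. Former placebo: 25 + 0 = 25. Under the dosing text the total is the same in both groups.

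**The case against.** The plan never defines a dose. Weeks 24 to 47 do contain 24 dosing occasions, and Study Design Overview speaks of weekly dosing through Week 24, which could make Phase I 25 occasions. This stands in part: the unit is undefined, and the syringe reading is inferred. It does not save the figure, because the occasion reading fits all the stated numbers only by counting Week 24 twice or adding a Week 48 dose.

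A stronger point concerns the consequence. The supply sentence says what the manufacturer will provide. It does not say that stock is packed per subject or cannot be replenished, and the totals assume that all 60 subjects finish although the plan allows for 10% dropout. If stock is pooled (an assumption) and one placebo subject leaves before Week 24, the other 19 need 19 × 25 = 475, which is within the stated 480. This stands: 20 short is a nominal gap, and no missed injection is shown.

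A reader might also infer that syringe counts would differ by group in Phase II, 25 against 24, and so reveal the Phase I assignment. The documents do not support that. They describe no kits, give no number of placebo syringes and state that the placebo syringes look identical, and the dosing text gives both groups 25 injections. A visible difference would arise only if the stated 24 were packed for each subject and the Week 24 placebo syringe were then added for former dupilumab subjects alone.

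Finally, the Amendment #1 description lists the Week 24 injection sentence as added for clarification, so the supply count may simply not have been updated. That may explain the mismatch, but it does not remove it from the current text.

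**Conclusion.** The supply figure for former placebo subjects is wrong as written when set against the plan's own Week 24 dosing text: 24 stated, 25 required, counted in 300 mg syringes. The syringe unit is the one that reproduces both dupilumab-arm figures without double counting or an undispensed dose. The size is one syringe per former placebo subject, or 20 in all at nominal arm sizes, full completion and a last injection at Week 47.

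The finding goes no further than that. A missed injection before Week 48 depends on fixed per-subject allotment with no spare stock, which the documents do not state. The primary endpoint is at Week 24, before any Phase II supply could run out, and type I error, power and sample size do not depend on this figure.

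**What to change.** Reconcile the supply sentence with the Week 24 dosing passages (the second paragraph of the supply section, the Visit 8 list and Table 1 footnote 12), and state whether the counts are doses or syringes. If the dosing passages stand, the Phase II figure for former placebo subjects becomes 25 and the nominal total becomes 2,460. Which passage should give way is for the sponsor and investigators to decide; no dosing is proposed here.

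The cost is one corrected number, one added definition and at most about 0.8% more drug. No analysis, endpoint or sample size changes.

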Matching placebo prefilled syringes (that will appear identical to the dupilumab syringes) will be provided by the company to the study sites. The subjects and the staff will remain unaware of the individual treatment assignment during the study. All study medication will be stored in a secure cool area between 2-8°C. Study drug will be administered to subjects at each study visit, with subsequent weekly injections performed by the patients at home. Patients (and/or caregivers) who are willing and able to administer dupilumab outside of the clinic will be trained on injecting study drug during the initial clinic visit.

We will query the subjects during each study visit on any missed injections and document this information. The investigative sites will account for all study drug dispensed and stored during the study.

STATISTICAL CONSIDERATIONS:

Sample Size Calculation

The primary outcome for this study is the SALT change at week 24. For patients with similar disease severity, a change in SALT of less than 5 units was observed ([name] et al, 2019). Assuming that dupilumab will induce a change in SALT of at least 25 units with a standard deviation of 10 at week 24, a sample size of 54 completed patients randomized 2:1 treatment to placebo (i.e. 36 in the treatment arm, 18 in the placebo arm) will provide 97% power to detect differences with Placebo based on a two-sided Student's t-test with a 0.05 type I error. Assuming that 10% of patients drop out of the study, we plan to enroll 60 total patients (i.e. 36 in the treatment arm, 18 in the placebo arm).

Demographics and Other Baseline Characteristics

Descriptive statistics of demographics and other baseline characteristics will be presented for all subjects and tabulated by treatment group. Presentations of age, sex, ethnicity, race and baseline will also be given. Other baseline characteristics include height, weight, and vital signs, duration of the AA and AD, concurrent diagnoses from medical history and indications for concomitant medication, concomitant medication, and previous AA and AD treatments.

Analysis of Primary Endpoint

A Mixed effect Model Repeated Measurement (MMRM) will be used to detect any overall differences in the treatment effect at week 24 compared to baseline.

Analysis of Secondary Endpoints

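### The stated 97% power does not follow from the printed sample-size inputs (above 99.99% if SD 10 applies to both arms), and the 60 enrolled are split as 36 + 18 = 54

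*Combined protocol and SAP*

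**What the plan says.** All the power inputs stand in one paragraph, under Statistical Considerations, Sample Size Calculation. For the comparator it cites a 2019 study of patients with similar severity, in whom "a change in SALT of less than 5 units was observed". For dupilumab it assumes a "change in SALT of at least 25 units with a standard deviation of 10 at week 24". From these it concludes that "a sample size of 54 completed patients randomized 2:1 treatment to placebo", that is 36 and 18, "will provide 97% power to detect differences with Placebo based on a two-sided" Student's t-test with type I error 0.05. It then allows for 10% dropout: "we plan to enroll 60 total patients (i.e. 36 in the treatment arm, 18 in the placebo arm".

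Three other places bear on this. Randomization and Blinding says: "Approximately 60 subjects will be enrolled in the study in order to have at least 54 subjects complete". Investigational Drug Supply and Blinding plans "dupilumab 300 mg for 40 subjects in Phase I and for all 60 subjects during Phase II", and counts 20 subjects as having been on placebo in Phase I. Analysis of Primary Endpoint names a different method from the one used for planning: "A Mixed effect Model Repeated Measurement (MMRM) will be used to detect any overall differences in the treatment effect at week 24".

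**The concern.** A difference of 20 units with an SD of 10 is two standard deviations. A comparison of that size with 54 patients should have power indistinguishable from 100%, so 97% looks out of line with its own inputs. This paragraph is the only justification for the sample size on the primary endpoint. If its result does not follow from its inputs, a reader cannot tell what comparator variability or what difference the trial was sized on. The split of the 60 enrolled is a separate matter: the two arm sizes given do not add up to the total.

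**Working it through.** **Inputs, all from Sample Size Calculation.** Dupilumab change 25 (stated as a minimum), SD 10; comparator change 5 (stated as an upper bound); 36 and 18 completers; two-sided t-test; alpha 0.05. The SD is attached to the dupilumab change only. Using 10 for placebo as well is an assumption, and it is the ordinary reading when a Student's t-test is quoted with one SD.

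**Attempt to reproduce 97%.**

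- Difference = 25 − 5 = 20.
- SE = SD × √(1/n₁ + 1/n₂) = 10 × √(1/36 + 1/18) = 2.887.
- Noncentrality = 20 / 2.887 = 6.93, with 36 + 18 − 2 = 52 degrees of freedom.
- Power from the noncentral t = 0.9999993 (type II error 6.6 × 10⁻⁷). The normal approximation gives 0.9999997.

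The 97% is not reproduced. A comparator change below 5 or a dupilumab change above 25 only raises the power; at a difference of 25 the type II error is 3.2 × 10⁻¹¹.

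**Other readings, with difference 20 and SD 10 unless noted.**

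| Variant | Power |
|---|---|
| One-sided test | above 99.99% |
| 40 and 20 patients | above 99.99% |
| 27 and 27 patients | above 99.99% |
| 32 and 16 patients | above 99.99% |
| Alpha 0.01 | above 99.99% |
| Alpha 0.001 | 99.95% |
| SD of change 10 × √2 = 14.14 | 99.8% |

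None comes to 97%. With the printed inputs and 2:1 allocation, 18 completers in total would already give 96.3%, and 21 would give 98.4%.

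**What 97% would require with 36 and 18.** The standardised difference must be 1.130 (1.110 for 96.5%, 1.153 for 97.5%), against 20/10 = 2.0. This can arise in several ways:

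- *SD 10 in both arms.* The difference is 11.30, so the comparator change is 25 − 11.30 = 13.70 (13.47 to 13.90 for anything that rounds to 97%). The plan says below 5.
- *One larger SD common to both arms.* About 17.7 at a difference of 20, or 22.1 at a difference of 25.
- *Dupilumab SD kept at 10, different placebo SD (by simulation).* At a difference of 20, a placebo SD of 23 gives 97.2% with the pooled t-test, and one of 20 gives 96.8% with the Welch test. At a difference of 25, 30 gives 97.1% (pooled) and 25 gives 97.2% (Welch). These placebo SDs appear nowhere in the documents; they show only how far from 10 the value would have to be.

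**Sensitivity to a common SD at difference 20.** SD 12 gives 99.99%, SD 15 gives 99.5%, SD 17.7 gives 97.0% and SD 20 gives 92.5%.

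**Enrolment split.** 54 / 0.9 = 60, so the dropout step is right. At 2:1, 60 × 2/3 = 40 and 60 × 1/3 = 20; after 10% dropout, 40 × 0.9 = 36 and 20 × 0.9 = 18. The printed enrolled split is 36 + 18 = 54, which is 6 short of 60 and identical to the completer split in the preceding sentence.

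**The case against.** The strongest reply is that the inputs are incomplete rather than inconsistent. The paragraph ties the SD of 10 to dupilumab alone, prints no placebo SD, gives bounds instead of the values entered, and does not say that the patients behind the comparator figure received placebo. A placebo SD taken from the cited study can be neither confirmed nor excluded from these documents. This stands, and it is why the figure above 99.99% is conditional on equal SDs. It does not rescue the paragraph: keeping every printed number needs a placebo SD two to three times the only SD printed, and a calculation that depended on such a value should have shown it.

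The second reply is that little follows in practice. On the ordinary reading the printed power is too low, which is the safe direction. On the other reading the power is right and only an SD is missing. Nothing in the documents suggests variability large enough to leave the trial short of power. The t-test is in any case a planning approximation to the MMRM. All of this stands and limits the point to a minor one.

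Third, the drug-supply section and the 2:1 ratio for 60 patients in Study Design Overview already settle the enrolment split. That is also right; the second 36/18 is a copying slip and adds no weight to the power point.

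**Conclusion.** Both parts hold, as minor errors. The 97% cannot be reproduced from what is printed. Assuming SD 10 in both arms and a difference of 20, the power is 0.9999993, a gap of 3.0 percentage points that no standard choice of formula, alpha or arm sizes closes. Either the power, the SD or the difference is misprinted, or a placebo SD of about 20 to 30 was used and not stated; the documents do not allow a choice between these. The finding does not show that the trial is underpowered or mis-sized. The enrolled split of 36 and 18 contradicts the total of 60 in its own sentence and the 40 and 20 in the drug-supply section.

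**What to change.** Revise the one paragraph. State the assumed change in each arm, the resulting difference and the SD in each arm as actually used, and say whether the comparator figure comes from placebo patients. Then give the power that follows from those inputs. If a difference of 20 and SD 10 in both arms are what was meant, it is above 99.99%. If a larger placebo SD was used, print it, with the form of t-test applied. Replace the second 36/18 with 40 dupilumab and 20 placebo enrolled, and keep 36/18 for completers. The cost is a wording change only: no further patients, visits or analyses.

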- The proportion of patients achieving at least 90% improvement in Severity of Alopecia Tool (SALT) score (SALT-90) at Weeks 24, 48 compared to Baseline.
- Change in the Alopecia Areata Symptom Impact Scale (AASIS) at Weeks 24 and 48 compared to baseline.
- Change in the Alopecia Areata Quality of Life questionnaire (AA-QoL) at Weeks 24 and 48 compared to baseline.
- Proportion of AA patients with Alopecia Areata Physician's Global Assessment (aaPGA) = 0-1 at Weeks 12, 24, 36, and 48 (see details in **Appendix 1**).
- Change in eyelash and eyebrow scores (see details in **Appendix 1**) at Weeks 12, 24, 36, and 48 compared to baseline.
- Change in eyelash and eyebrow scores (see details in **Appendix 1**) at Week48 compared to Week24.
- Change from baseline in Eczema Area and Severity Index (EASI) at Weeks 12, 24, 36, and 48 (see details in **Appendix 1**).
- Change from week 24 in EASI at weeks 36 and 48 (see details in **Appendix 1**).
- Proportion of patients with Eczema Area and Severity Index (EASI)-50 ($\geq 50\%$ reduction from baseline in EASI scores) at Weeks 12, 24, 36, and 48.
- Proportion of patients with Eczema Area and Severity Index (EASI)-75 ($\geq 75\%$ reduction from baseline in EASI scores) at Weeks 12, 24, 36, and 48.
- Proportion of patients with Eczema Area and Severity Index (EASI)-90 ($\geq 90\%$ reduction from baseline in EASI scores) at Weeks 12, 24, 36, and 48 (see details in **Appendix 1**).
- Semi-quantitative score using SALT subclasses (0 = no hair loss; 1 = $<25\%$ hair loss; 2 = 25-49% hair loss; 3 = 50-74% hair loss; 4 = 75-99% hair loss; 5 = 100% hair loss).
- Safety profile of dupilumab in subjects with AA by reported adverse effects, physical examinations and laboratory parameters.

Mechanistic (Exploratory) Endpoints

[figure not shown]
- Determine the effect of dupilumab therapy on the immune cell populations (e.g. T cells, dendritic cells, eosinophils, and mast cells) and related cytokines, chemokines, and inflammatory cells found in the blood and skin of study subjects. RT-PCR will be used to determine these effects.

STUDY DESIGN OVERVIEW:

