A Mixed effect Model Repeated Measurement (MMRM) will be used to detect any overall differences in the treatment effect at week 48 compared to baseline, as well as at week 48 compared to week 24. This formulation intrinsically models the within patient correlation structure as in the case of a paired t-test. This approach introduces less bias than restricting the analysis for those patients who completed the study. A similar model will be used to evaluate the change in eyelashes and eyebrows scores, as well as in Eczema Area and Severity Index (EASI) at each visit compared to baseline.

A two-sided Fisher exact test will be used to compare the percentage of patients who achieve 50% improvement in SALT, eyelashes, eyebrows and EASI scores (calculated as $100 \times (\text{SCORE}_{\text{baseline}} - \text{SCORE}_{\text{W24}}) / \text{SCORE}_{\text{baseline}}$) between drug and placebo groups. The same approach will be used for other discrete variables, SALT-75, and SALT-90 at each visit compared to baseline.

Analysis of Exploratory Endpoints

The change from Baseline in molecular markers in skin biopsies after treatment will be analyzed using a mixed effect linear model with treatment and time interaction as a fixed effect and a random effect for each patient. This formulation intrinsically models the within patient correlation structure as in the case of a paired t-test, and introduces less bias than restricting the analysis for those patients who completed the study.

Analysis of Mechanistic Endpoints

For comparison of expression levels of lesional, and non-lesional AA skin, we will use RT-PCR by Taqman Low-density arrays and RNA-sequencing. RT-PCR values will be normalized to the housekeeping gene RPLP0 (validated in our AD and AA studies) and log-2 transformed prior to analysis. RNA-sequencing data will be pre-processed using standard pipeline (exhaustively used by our group in a large number of studies) and log-2 voom-transformed expression. Mixed effect model will be used and p-values for the moderated t-tests and paired-t-test will be adjusted by Benjamini-Hochberg procedure.

Extensive bioinformatics tools will be employed to gain insights into the results and test hypotheses that are generated in the “data mining stage”. This will include (but will not be limited to) pathway and gene-set enrichment analyses using Ingenuity software, GSEA, the R package GSVA (Gene Set Variation Analysis) and other in-house codes produced

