Appendix 1. Clinical Assessments/Scoring

Alopecia Areata Assessments:

Severity of Alopecia Tool (SALT)

Scalp divided into four areas: vertex (40% of scalp surface area), right profile (18% of scalp surface area), left profile (18% of scalp surface area), and posterior scalp (24% of scalp surface area). Percentage of hair loss in these areas is multiplied by percent surface area of the scalp in that area. SALT score is the sum of percentage of hair loss in all areas.

SALT score:

	Left Side (18%)	Right Side (18%)	Top (40%)	Back (24%)	
Percentage Hair Loss					
Percentage X Area	X 0.18	X 0.18	X 0.4	X 0.24	
Total	+	+	+	=	

Eyelash/Eyebrow Assessment Score

0= None

1= Minimal eyelashes/eyebrows

2= Moderate eyelashes/eyebrows

3= Prominent eyelashes/eyebrows

4= Very prominent eyelashes/eyebrows

Alopecia Areata Physician's Global Assessment (aaPGA):

The aaPGA is used to assess the clinical response to treatment based on a 6-point scale ranging from 0 (no regrowth) to 5 (100% regrowth):

No regrowth	<25% regrowth	25-49% regrowth	50-74% regrowth	75-99% regrowth	100% regrowth
0	1	2	3	4	5

Atopic Dermatitis Assessments:

Scoring atopic dermatitis (SCORAD)

3 components: A) % body surface area involvement (the rule of 9's); B) Intensity of eczema evaluated on representative lesions, rating 5 lesions (scale 0 to 3) for features including erythema, thickness, excoriations, wound/scab formation, lichenification, and xerosis; C) Functional impact based on pruritus (0 to 10) and sleep disturbance (0 to 10). Final score determined by $SCORAD = A/5 + (7 \times B/2) + C$

SCORAD INDEX
[RULE OF 9'S]

ANTERIOR INFANT POSTERIOR

A: EXTENT Please indicate the area involved 	A/5 + 7B/2 + C 
B: INTENSITY 	
C: SUBJECTIVE SYMPTOMS PRURITUS + SLEEP LOSS 	

CRITERIA	INTENSITY
Erythema	
Oedema/Papulation	
Oozing/crust	
Excoriation	
Lichenification	
Dryness*	

* Dryness is evaluated on uninvolved areas

MEANS OF CALCULATION
INTENSITY ITEMS (average representative area)
0 = absence
1 = mild
2 = moderate
3 = severe

VAS

Init: _____ ID # _____

Date: _____

Subject VAS:

Draw a vertical line across the present line to represent the average for the last 3 days or nights regarding how much itching and sleep loss you have experienced:

Itching:

Sleep Loss:

Eczema Area and Severity Index (EASI)

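### The printed 50%-improvement formula counts the loss of half or more of an eyelash or eyebrow score as a response, never counts a gain, and cannot score patients who start at 0

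*Combined protocol and SAP*

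**What the plan says.** Under Statistical Considerations, Analysis of Secondary Endpoints, the plan states "A two-sided Fisher exact test will be used to compare" the "percentage of patients who achieve 50% improvement in SALT, eyelashes, eyebrows and EASI scores" between drug and placebo. A single formula in parentheses defines improvement for all four scores: 100 × (baseline score − Week 24 score)/baseline score.

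Appendix 1 gives the direction of each scale:

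- SALT adds up percentage hair loss over the scalp areas, so higher is worse.
- EASI grades its signs from absent to severe, so higher is worse.
- The eyelash/eyebrow score starts at 0 for no hair, continues with "1= Minimal eyelashes/eyebrows" and ends with "4= Very prominent eyelashes/eyebrows", so higher is better.

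The part of the endpoint list available for this review names the lash and brow outcome as "Change in eyelash and eyebrow scores". The statistical section analyses that separately: "A similar model will be used to evaluate the change in eyelashes and eyebrows scores".

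**The concern.** The formula is positive only when a score falls. For lashes and brows a fall is hair loss, so a program that follows the text would label patients who lost hair as responders and would count no patient who gained. The Fisher comparison would then credit the arm with more substantial loss.

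The zero baseline is a second problem. The protocol background describes alopecia universalis as loss of all scalp and body hair. These patients are eligible, and the Study Design Overview lets totalis and universalis together make up as many as 30 of the 60 subjects. Some baseline lash or brow scores of 0 are therefore foreseeable. These patients have the most to regain, and the printed rule cannot score them.

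**Working it through.** There is no stated figure to reproduce; the check is of the response definition itself.

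**Inputs.** Formula and four scores: Analysis of Secondary Endpoints. Scale 0 to 4: Appendix 1. Arm sizes for the illustration ("36 in the treatment arm, 18 in the placebo arm"): Sample Size Calculation.

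**Step 1: printed formula.** With baseline B and Week 24 score W, improvement is 100 × (B − W)/B, and response is taken as 50 or more. All 25 score pairs:

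| B | W=0 | W=1 | W=2 | W=3 | W=4 |
|---|---|---|---|---|---|
| 0 | undefined | undefined | undefined | undefined | undefined |
| 1 | 100 | 0 | −100 | −200 | −300 |
| 2 | 100 | 50 | 0 | −50 | −100 |
| 3 | 100 | 66.7 | 33.3 | 0 | −33.3 |
| 4 | 100 | 75 | 50 | 25 | 0 |

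- Gains from a non-zero baseline: 0 of 6 count. For example, 1→4 gives 100 × (1 − 4)/1 = −300.
- Losses: 8 of 10 count. For example, 4→2 gives 100 × (4 − 2)/4 = +50. Only 4→3 and 3→2 fall short.
- No change: 0%, not a response.
- Baseline 0: all 5 pairs are undefined, including the 4 gains.

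Direction check on SALT: 80→40 gives 100 × (80 − 40)/80 = +50, as intended.

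**Step 2: the sign alone reversed,** 100 × (W − B)/B. Baseline 0 is still undefined. Baseline 3 can reach at most +33.3% and baseline 4 at most 0%. Only 5 of the 10 possible gains count (1→2, 1→3, 1→4, 2→3, 2→4).

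**Step 3: printed formula applied to 4 − score,** which reduces to 100 × (W − B)/(4 − B):

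| B | W=0 | W=1 | W=2 | W=3 | W=4 |
|---|---|---|---|---|---|
| 0 | 0 | 25 | 50 | 75 | 100 |
| 1 | −33.3 | 0 | 33.3 | 66.7 | 100 |
| 2 | −100 | −50 | 0 | 50 | 100 |
| 3 | −300 | −200 | −100 | 0 | 100 |
| 4 | undefined | undefined | undefined | undefined | undefined |

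Of the 10 possible gains 8 count (0→1 and 1→2 do not). Of the 6 losses from baselines 1 to 3 none counts. Only baseline 4 is undefined.

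**Step 4: what this could do to the test.** The patient counts are hypothetical. Assume 36 versus 18 patients, all with baselines 1 to 3. Nine dupilumab patients go 2→3 and no dupilumab patient loses half the score; k placebo patients do.

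| Rule | Dupilumab | Placebo | Two-sided Fisher p |
|---|---|---|---|
| Printed, k = 2 | 0/36 | 2/18 | 0.107 |
| Printed, k = 3 | 0/36 | 3/18 | 0.033, favouring placebo |
| Printed, k = 4 | 0/36 | 4/18 | 0.010, favouring placebo |
| 4 − score | 9/36 | 0/18 | 0.022, favouring dupilumab |

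The k = 3 value is C(18,3)/C(54,3) = 816/24,804 = 0.033, since every other table with three responders is more probable. If one dupilumab patient also loses half, the printed rule gives p = 0.103 for k = 3 and 0.038 for k = 4. If half of each arm starts at 0 and drops out of the calculation, 0/18 versus 3/9 gives p = 0.029.

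**The case against.** The strongest reply is that the sentence speaks of improvement, so a competent analyst would notice the mismatch and would not report lost brows as a benefit. That is likely, but noticing it does not settle the replacement. Steps 2 and 3 show that two natural repairs give different responder sets (5 against 8 of the 10 gains). Data Transfer and Management sends clinical scores and the allocation code to the biostatistical team, so a repair chosen at analysis could be chosen with the results in view.

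The reach is small, and that stands. Lash and brow endpoints appear in the available list only as change in score, and the mixed model for change does not use this formula. Part of the endpoint section was not available, so whether a 50% lash/brow response is also listed there could not be checked. The statistical section prespecifies the test either way.

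The illustration is sensitive to its assumptions, and that also stands. With one placebo patient losing half, p = 18/54 = 0.33. If the nine dupilumab gains were 1→2 instead of 2→3, the 4 − score rule would count 0/36. The p-values show that a reversal is possible, not that it is likely.

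Reverse-coding is not the only possible definition. It treats 4 as the state with no deficit, which Appendix 1 does not say is normal, and it weights one-step gains unevenly. A fixed-step gain or a target score would also remove the contradiction. None of this makes the printed rule right. A possible zero EASI baseline in subjects whose dermatitis is historical only is a separate matter.

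**Conclusion.** The concern holds: the rule is wrong as written for eyelashes and eyebrows, and should be corrected. Of the 20 score pairs it can evaluate, it classes 8 as responses, and all 8 are losses of at least half the baseline score. The 5 pairs starting from 0 cannot be evaluated.

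These are counts of possible score pairs, not of patients. The documents give no baseline lash or brow distribution and no number of subjects starting at 0, so the effect on the trial's result cannot be sized. The cap of 30 covers totalis and universalis together and is an upper limit, and totalis need not involve lashes or brows.

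The conclusion rests on reading the formula as applying to every score named in its sentence, and on the absence of any reverse-coding or zero-baseline rule in the text available.

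**What to change.** Keep the printed formula for SALT and EASI. For eyelashes and eyebrows, state that the same formula and 50% threshold apply to the reverse-coded score, 4 − score, among subjects with a baseline score of 0 to 3. Record this before unblinding.

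The cost is a change of analysis wording. The scores are already collected at every visit, and no visit, procedure or sample size changes. Two consequences should be stated alongside it. Subjects at baseline 4, who have no deficit to improve on this scale, leave the lash/brow responder denominator. One-step gains from 0 or 1 do not reach 50%, although they still contribute to the mixed model of change.
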